1 PROTOCOL SUMMARY

1.1 SYNOPSIS

Title:	A Single-Site, Parallel-Group, Randomized-Controlled Trial of Navigation Versus Usual Care for The Management of Delays and Racial Disparities Starting Postoperative Radiation Therapy in Adults with Surgically-Managed, Locally Advanced Head and Neck Squamous Cell Carcinoma (NDURE 2.0)
Grant #:	K08 CA237858
Study Description:	In this study, we evaluate the feasibility, acceptability, preliminary clinical impact, and preliminary behavioral impact of NDURE (Navigation for Disparities and Untimely Radiation thErapy), a navigation-based, multilevel intervention (MLI) targeting barriers to timely, guideline-adherent PORT at the patient-, healthcare team-, and organization-levels to improve timely, equitable post-operative radiation treatment (PORT) among patients with Head and Neck Squamous Cell Carcinoma (HNSCC). We hypothesize that NDURE will be feasible, acceptable, improve the timeliness of PORT for white and African American (AA) HNSCC patients and decrease disparities in delay between the two groups by improving multi-level health behavior constructs.
Objectives:	
Primary Objective (NDURE feasibility study): To assess the feasibility of NDURE among white and AA HNSCC patients with respect to accrual.
 
Secondary Objectives (NDURE feasibility study):
 
 1. To assess the feasibility of NDURE among white and AA HNSCC patients with respect to NDURE completion. 2. To assess the acceptability of NDURE among HNSCC patients and providers 3. To characterize navigator caseload and time allocation delivering the NDURE intervention. 4. To describe the preliminary clinical efficacy of NDURE on delays starting PORT among white and AA patients with HNSCC. 
Primary Objective (RCT of NDURE vs Usual Care): To evaluate the preliminary clinical impact of NDURE compared with usual care (UC) on delays starting PORT among white and AA HNSCC patients.
 
Select Secondary Objectives (RCT of NDURE vs Usual Care):
 
 1. To evaluate the preliminary clinical impact of NDURE compared with UC on time-to-PORT among white and AA HNSCC patients. 2. To evaluate the preliminary clinical impact of NDURE compared with UC on racial disparities in delays starting PORT among white and AA HNSCC patients 3. To evaluate the preliminary impact of NDURE compared with UC on cancer care delivery processes. 
Exploratory Objectives (RCT of NDURE vs Usual Care):
 
 1. To explore the preliminary clinical impact of NDURE compared with UC on decreasing barriers to timely PORT. 2. To explore the preliminary behavioral mechanism of action of NDURE.

Endpoints:	
Primary Endpoint (NDURE feasibility study): NDURE Accrual Rate
 
Secondary Endpoints (NDURE feasibility study): Navigator Caseload Navigator Time Allocation (Direct) Navigator Time Allocation (Indirect) Patient Satisfaction with the Interpersonal Relationship with the Navigator Scale PORT delay
 
Primary Endpoint (RCT of NDURE vs Usual Care): PORT delay
 
Select Secondary Endpoints (RCT of NDURE vs Usual Care): Time-to-PORT Initiation Treatment Package Time
 
Pre-Surgical radiation consultation Pre-Radiation therapy dental extractions Time from surgery to PORT referral Time from surgery to postoperative appointment with radiation oncology

Study Population:	The study population will consist of patients 18 years of age or older, male and female sex, and self-identified white and AA race, with locally advanced HNSCC undergoing curative intent surgery followed by PORT with or without concurrent chemotherapy.
Phase/Stage:	N/A
Description of Sites:	The study will be conducted, and participants enrolled, at the Medical University of South Carolina (MUSC) Hollings Cancer Center (HCC) Head and Neck Tumor Center.
Description of Study Intervention:	NDURE is a navigation-based, MLI targeting barriers to timely, guideline-adherent PORT at the patient-, healthcare team-, and organization-levels to decrease delays and racial disparities starting guideline-adherent PORT. NDURE will be delivered from surgical consultation to PORT initiation (~3 months). The three NDURE navigation sessions, which are expected to take 30-60 minutes each, will coincide with the presurgical consult, hospital discharge, and 1 st postoperative clinic visit, time points chosen to facilitate case identification and coordination across key care transitions.
Study Duration:	NDURE Feasibility: 7 months NDURE vs Usual Care RCT: 42 months
Participant Duration:	3 months

1.2 SCHEMA

1.2.1 NDURE FEASIBILITY STUDY

[figure not shown]

Figure 1. Feasibility Study Schema. Following completion of baseline questionnaires, participants (n=15) will be enrolled into NDURE. Measures of feasibility will be assessed during intervention delivery. Following completion of the NDURE intervention, acceptability will be assessed via validated measures satisfaction with patient navigation, a study-specific program evaluation, and semi-structured interviews with patients and providers. Preliminary clinical efficacy of NDURE on delays starting PORT will be described.

1.2.2 RCT OF NDURE VERSUS USUAL CARE

[figure not shown]

Figure 2. RCT Schema. HNSCC patients undergoing surgery and PORT will be enrolled into a pilot RCT comparing NDURE to usual care to evaluate the preliminary clinical impact of NDURE on delays and racial disparities starting PORT after HNSCC surgery.

1.3 SCHEDULE OF ACTIVITIES

Table 1. Schedule of Activities for NDURE and Usual Care: Screening, Treatment, and Follow-up								
Study Period		Screening	Allocation	Treatment			Follow-Up	
Visit Label	Visit #			Pre -Op	Pre - D/ C	Post - D/C		
Visit Label	Visit #	1	--	2	3 ^{a,b}	4 ^c	5 ^d	6 ^e
Study Activity								
Enrollment	Eligibility Screen	X						
	Informed Consent	X						
Allocation	Allocation		X					
Study Intervention	NDURE			X	X	X	X	
	Usual Care			X	X	X	X	
Study Assessments								
Baseline	Demographics	X						
	Baseline Oncologic Characteristics	X						
	Charlson-Deyo Comorbidity Index	X						
	PORT Delay Nomogram	X						
	Lukwago Cultural Questionnaire	X						
Safety	Adverse Events			←		→		
Efficacy	Surgical Details				X			
	PORT Start Date						X	
Fidelity	NDURE Fidelity						X	
Feasibility	NDURE Accrual	X						
	NDURE Completion			X	X	X	X	
	Navigator Caseload			←		→		
	Navigator Time Allocation			X	X	X	X	
Acceptability	PSN-I Questionnaire						X	
	Semi-Structured Interview						X	
	Program Evaluation Questionnaire						X	
Barriers to Timely PORT	PBQ-Patient Questionnaire			X	X	X	X	
	PBQ-Navigator			X	X	X	X	
	Presurgical RT Consult						X	
	Pre-RT Dental Extractions						X	

Table 1. Schedule of Activities for NDURE and Usual Care: Screening, Treatment, and Follow-up								
Study Period		Screening	Allocation	Treatment			Follow-Up	
Visit Label	Visit #			Pre-Op	Pre-D/C	Post-D/C		
		1	—	2	3 ^{a,b}	4 ^c	5 ^d	6 ^e
Study Activity								
Cancer Care Delivery Processes	Date Pathology Report Returned						X	
	Date of Postoperative Referral to Radiation Oncology						X	
	Date of Postop Appointment with Radiation Oncology						X	
	Date of CT Simulation						X	
Adjuvant Therapy Details	Type of Adjuvant Therapy						X	
	PORT Completion Date						X	
	Radiation and Medical Oncology Facility						X	
Health Behavior Constructs	CTM-15 Questionnaire				X	X		
	ISEL-12 Questionnaire	X					X	
	PSQ Questionnaire	X			X	X		
	IPQ-R Consequences Questionnaire	X			X	X		
	CASE-Cancer Questionnaire	X					X	
Abbreviations: CASE: Communication & Attitudinal Self-Efficacy Scale; CT: Computed Tomography; CTM-15: Care Transition Measures-15; d: days; IPQ-R: Illness Perception Questionnaire-Revised; ISEL-12: Interpersonal Support Evaluation List-12; NDURE: Navigation for Disparities and Untimely Radiation ThErapy; PBQ: Perceived Barriers Questionnaire; PORT: Postoperative Radiation Therapy; PSN-I: Patient Satisfaction with the Interpersonal Relationship with the Navigator Scale; PSQ: Perceived Susceptibility Questionnaire; Rad Onc: Radiation therapy RT: Radiation therapy								
^a If the discharge date is expected to be > 21 days after surgery, then complete all Study Visit 3 assessments (except CTM-15) on postoperative day 21. If the patient is unable to complete the assessments on postoperative day 21 (due to mental status), then complete on the 1 st day after postoperative day 21 in which the mental status allows completion of the assessments. If the patient is subsequently discharged after postoperative day 21, then the CTM-15 can be completed on the time of discharge. If the patient is never discharged prior to PORT, then the CTM-15 is omitted.								
^b For patients undergoing transoral robotic surgery and staged neck dissection, Study Visit 3 assessments should be completed after the second hospitalization (regardless of the order of transoral robotic surgery and the neck dissection).								
^c If the participant is never discharged from the hospital postoperatively prior to starting PORT, Study Visit 4 intervention and assessments are omitted.								

Table 1. Schedule of Activities for NDURE and Usual Care: Screening, Treatment, and Follow-up							
Study Period	Screening	Allocation	Treatment				Follow-Up
			Pre -Op	Pre - D/ C	Post - D/C	Start of PORT	
Visit Label			1	2	3 ^{a,b}	4 ^c	5 ^d
Visit #							6 ^e
Study Activity							

^a Study Visit 5 assessments are to be administered after the start of PORT. For the purposes of determining when to administer Study Visit 5 assessments, the study coordinator will determine that a patient has started PORT either by verifying in the EMR (for patients undergoing PORT at MUSC) or by contacting the patient no sooner than 8 weeks after surgery (for patients undergoing PORT outside of MUSC). If PORT is indicated but never initiated, Study Visit 5 assessments are to be completed 12 weeks after surgery.
 
^b Following completion of PORT, the study coordinator will gather all of the required source documentation to ascertain efficacy and cancer care delivery endpoints as well as adjuvant therapy details
							

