4.2.3 JUSTIFICATION FOR INTERVENTION

4.2.3.1 JUSTIFICATION FOR THE MODE OF DELIVERY

PN is a patient-centered intervention that addresses barriers to cancer care, thereby improving the delivery of timely, equitable cancer screening, decreasing racial differences in post-screening diagnostic resolution, and decreasing care fragmentation^{10,25-27}. Although technology-enhanced interventions are increasingly common to facilitate care coordination, PN at its heart is still a patient-centered intervention and is delivered in person via face to face interactions. Face to face interactions can unduly burden patients and result in decreased intervention adherence. In addition, face to face interactions are being minimized to promote patient and healthcare worker safety during the COVID-19 pandemic.

The preferred method for delivering NDURE is face to face. However, due to changes in healthcare delivery necessitated by COVID-19 pandemic, it is permissible for the NDURE navigator to use a telemedicine videoconferencing platform for NDURE sessions 1 or 3 (study visit 2 or 4). The number, frequency, and timing of intervention contacts (see details in **Section 4.2.3.2, Justification for Number, Frequency, and Timing of Intervention Contacts**) were carefully chosen to minimize potential concerns that may arise from face to face interactions. In addition, supplemental contact beyond the three prescribed sessions will occur with a frequency and modality (e.g. text message, email, etc.) dictated by patient and navigator need.

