6.1.2 ADMINISTRATION AND/OR DOSING

6.1.2.1 NDURE

NDURE will be delivered in one-on-one, face-to-face sessions between the navigator and the participant in a clinic- or hospital-based setting. The NDURE intervention consists of three navigation encounters (Study Visits 2-4), which are expected to take 30-60 minutes each. The NDURE navigation encounters (Study Visits 2-4) will coincide with the presurgical consult, hospital discharge, and 1st postoperative clinic visit (see Section 1.3, Schedule of Activities). These time points were chosen to facilitate case identification and coordination across key care transitions. Contact beyond the three prescribed sessions will occur with a frequency and modality (e.g. text message, email, etc.) dictated by patient and navigator need. The NDURE intervention will be delivered in the following settings: the MUSC Head and Neck Tumor Center and MUSC hospital. A single dedicated navigator with no competing clinical or administrative responsibilities outside of this trial will deliver the NDURE intervention. Full dose of the NDURE intervention will consist of completing all three navigation sessions. Because the administration schedule and dose of usual care is highly variable, the NDURE intervention will not be dose-matched to usual care on intensity, duration, and/or frequency. Participants in the trial are permitted to interact with other participants after randomization, regardless of treatment allocation. Such encounters may occur in waiting rooms before or after clinic appointments given the single-site design of the trial.

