6.4 STUDY INTERVENTION/EXPERIMENTAL MANIPULATION ADHERENCE

Participants' adherence with study procedures will be tracked by attendance at intervention visits. All study visits are mandatory to remain an active participant. Adherence to attendance at Visits 2-4 will be ascertained from the NDURE visit note authored by the navigator that is available in the EMR. Adherence to attendance at Visits 1 and 5 will be ascertained from the REDCap data collection form. Adherence to attendance at visits 1-5 will be documented in the electronic Case Report Form (eCRF).

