9 STATISTICAL CONSIDERATIONS

9.1 STATISTICAL HYPOTHESES

9.1.1 SINGLE ARM FEASIBILITY STUDY

NDURE Accrual (Primary Endpoint)

We hypothesize that at least 60% of eligible subjects for the NDURE study will accrue to the study. Alternatively, our null hypothesis is that less than 60% of eligible subjects for the NDURE study will accrue to the study.

The preliminary feasibility analysis will be calculated for the secondary endpoint using the first 25 patients eligible to accrue to the study, which is expected to occur over 4 months.

NDURE Completion (Secondary Endpoint)

We hypothesize that at least 85% of subjects who enroll in the NDURE study (at least 13 of 15 subjects) will complete all 3 NDURE sessions. Alternatively, our null hypothesis is that less than 13 of the 15 subjects who enroll in the NDURE study will complete all 3 NDURE sessions

The preliminary feasibility analysis will be calculated for the secondary endpoint using the first 15 patients who accrue to the study, which is expected to occur over 6 months.

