9.2 SAMPLE SIZE DETERMINATION

9.2.1 NDURE FEASIBILITY STUDY

Power and sample size calculations were performed using the University of Iowa Binomial Distribution applet. The sample size justification for this single-arm study is based on the primary feasibility endpoints of NDURE accrual and completion. In the RCT of NDURE, we plan to enroll 60% of eligible patients. We expect similar accrual in this feasibility study. Therefore, we hypothesize that at least 60% of eligible subjects for the NDURE study will accrue to the study. Alternatively, our null hypothesis is that less than 60% of eligible subjects for the NDURE study will accrue to the study. Accruing to NDURE will be considered feasible if at least 15 of 25 eligible subjects enroll. Our sample size for the feasibility study was selected to provide a small probability of having an observed accrual rate of at least 60% when the true accrual probability is actually less than 60%. For example, if the true accrual probability for our proposed design is 45% (35%), the probability of enrolling 15 or more of 25 eligible subjects is only 10% (1%). Additionally, we hypothesize that at least 85% of subjects who enroll in the NDURE study will complete all 3 NDURE sessions. Alternatively, our null hypothesis is that less than 85% of subjects who enroll in the NDURE study will complete all 3 NDURE sessions. That is to say, NDURE will be considered feasible if at least 13 of the 15 subjects enrolled complete all three NDURE sessions. Accordingly, our sample size for the single-arm study was selected to provide a small probability of having an observed completion rate of at least 85% when the true completion probability of the intervention is actually less than 85%. For example, if the true completion probability for our proposed design is 70% (60%), the probability that 13 or more of the 15 enrolled patients complete all three NDURE sessions is 13% (3%). Therefore, the probability of falsely declaring NDURE feasible is reasonably controlled based on this sample size.

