3. Have an indication for PORT per NCCN Guidelines based on the presence of at least one of the following adverse features on final pathologic evaluation: ENE, positive margin, pT3 or pT4 primary, at least pN1 nodal disease (per AJCC 8th edition for p16-ve non-oropharyngeal SCC or AJCC 7th edition for p16+ve oropharyngeal SCC), nodal disease in levels IV or V, PNI or LVI

Analysis will be performed based on assignment at randomization regardless of the intervention received (modified intent to treat). This analysis set will be used for analysis of the secondary endpoint TTP.

The **treatment package time (TPT) analysis set** is the TTP analysis set restricted to patients who have initiated PORT.

The **full analysis set (FAS)** is the set of all trial participants who enroll and are eligible for the study. Patients who enroll but subsequently drop out prior to receiving any of the assigned intervention will be replaced. The FAS will be used for evaluation of the pre-surgical radiation consultation, and for secondary analyses of both the primary endpoint and secondary endpoints.

The **dental evaluation prior to surgery analysis set** will be the FAS restricted to patients who receive curative intent surgery at MUSC and are indicated for dental evaluation.

The **extraction of indicated teeth analysis set** is the subset of patients in the dental evaluation prior to surgery analysis set who are indicated for dental extractions prior to surgery.

The **time from surgery to PORT referral scheduling analysis set** and **time from surgery to appointment with radiation oncology analysis set** are equivalent to the TTP analysis set.

The **Per protocol set** is composed of all patients enrolled in the trial who have completed all 3 of the ENDURE intervention sessions as described in the protocol. This analysis set will be used for secondary analyses of both the primary endpoint and secondary endpoints.

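### The schedule drops NDURE session 3 for patients never discharged before PORT, yet section 9's completion rule and per-protocol set require all three sessions without exception

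*Combined protocol and SAP*

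**What the plan says.** **Schedule.** Table 1, footnote c (section 1.3): "If the participant is never discharged from the hospital postoperatively prior to starting PORT, Study Visit 4 intervention and assessments are omitted". The footnote removes the intervention contact as well as the questionnaires. Section 4.2.3.1 shows which session this is by pairing "NDURE sessions 1 or 3 (study visit 2 or 4"), so Visit 4 is session 3.

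**Dose.** Section 6.1.2.1: "The NDURE intervention consists of three navigation encounters (Study Visits 2-4"), and "Full dose of the NDURE intervention will consist of completing all three navigation sessions".

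**Completion.** The feasibility hypothesis in 9.1.1 is that "at least 13 of 15 subjects) will complete all 3 NDURE sessions". The decision rule in 9.2.1 is that "at least 13 of the 15 subjects enrolled complete all three NDURE sessions". Section 9.4.4.1 analyses the percentage of enrolled patients who attend all three sessions and, as a second measure, the proportion of the three sessions completed. Section 8.4.1 differs: its completion rate needs the baseline assessment, two or more sessions and the final follow-up assessment.

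**Per-protocol set.** Section 9.3 restricts it to patients "who have completed all 3 of the ENDURE intervention sessions as described in the protocol" and uses it for secondary analyses of the primary and secondary endpoints.

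**Adherence.** Section 6.4: "All study visits are mandatory to remain an active participant".

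**The concern.** The schedule foresees a group of participants for whom session 3 is not delivered. The analysis sections have no provision for them. Someone who receives everything Table 1 schedules is counted under section 9 in the same way as someone who did not attend.

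Two results are exposed. In the feasibility study, the 13-of-15 rule tolerates only two non-completers, so a long hospital stay can use up that allowance without saying anything about whether NDURE sessions can be delivered. In the RCT, the per-protocol set drops NDURE patients on the basis of a post-randomisation event. Section 8.5.1 says that post-surgical toxicity is associated with PORT delay, and patients still in hospital when PORT starts plausibly carry more of it. If their delay rate exceeds the arm average, removing them lowers the NDURE per-protocol delay rate.

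**Working it through.** **1. How many sessions are possible.** Sessions 1, 2 and 3 are Visits 2, 3 and 4 (4.2.3.1, 6.1.2.1). Footnote c removes Visit 4, so the maximum is two.

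**2. How such a patient is classified** (Visits 2 and 3 attended, baseline and final follow-up done):

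| Section | Requirement | Result |
|---|---|---|
| 6.1.2.1 full dose | three sessions | not full dose |
| 9.1.1, 9.2.1 13-of-15 rule | three sessions | non-completer |
| 9.4.4.1 first measure | three sessions | non-completer |
| 9.4.4.1 second measure | share of three sessions | 2/3 |
| 8.4.1 completion rate | at least two sessions | complete |
| 9.3 per-protocol set | three sessions | excluded |
| 9.3 PORT delay analysis set | no session requirement | unaffected |

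**3. The plan's own figures.** Section 9.2.1 gives the probability of 13 or more completers among 15 as 13% (3%) for a true completion rate of 70% (60%). The exact binomial tail P(X ≥ 13), X ~ Bin(15, p), gives 0.127 at p = 0.70 and 0.027 at p = 0.60, so both are reproduced.

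**4. Effect on the 13-of-15 rule.** Let c be the probability of completing all applicable sessions and q the probability of never being discharged before PORT. Both are assumptions, taken as independent. Judged on applicable sessions, the chance of passing is P(X ≥ 13) at p = c. Under section 9 as written it is P(X ≥ 13) at p = c(1 − q). With c = 0.90:

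| q | c(1 − q) | P(at least 13 of 15) |
|---|---|---|
| 0% | 0.900 | 82% |
| 1% | 0.891 | 78% |
| 5% | 0.855 | 63% |
| 10% | 0.810 | 44% |

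**5. Effect on the NDURE per-protocol delay rate.** Inputs: 75 patients and 25% delayed (the design values in 9.2.2), so 18.75 expected delays. With k patients excluded, the rate is (18.75 − k)/(75 − k) if all of them are delayed and (18.75 − k/2)/(75 − k) if half are. To isolate this effect, no other exclusions are assumed.

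| k | k/75 | All delayed | Half delayed |
|---|---|---|---|
| 1 | 1.3% | 17.75/74 = 24.0% | 18.25/74 = 24.7% |
| 2 | 2.7% | 16.75/73 = 22.9% | 17.75/73 = 24.3% |
| 4 | 5.3% | 14.75/71 = 20.8% | 16.75/71 = 23.6% |
| 6 | 8.0% | 12.75/69 = 18.5% | 15.75/69 = 22.8% |

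The all-delayed column is the extreme case. Footnote c says only that PORT began before discharge, not that it began after day 42.

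**The case against.** The strongest reply is that the case is rare and the consequences are secondary. Section 4.2.3.2 expects attendance at the three visits to be close to 100%, and section 5.5 puts the likelihood of contact at about the same level. That stands: the low end of each range is the more plausible, and there the effect is small.

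A reader might infer that a patient managed to schedule can never be complete. The documents do not support this, because 8.4.1 accepts two sessions and the second measure in 9.4.4.1 gives credit for two of three. But 8.4.1 does not govern the 13-of-15 rule or the per-protocol set, so the same patient is complete in one section and incomplete in another.

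A reader might also infer that the trial's main result is tilted towards NDURE. It is not. The primary analysis in 9.3 and 9.4.3.2 follows randomised assignment, whatever intervention was received. Even for the per-protocol analysis the direction of bias is not settled: the set is defined by completed NDURE sessions, and no rule says how usual-care patients enter it.

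Section 6.4 is weak evidence of a contradiction, since a visit omitted by footnote need not be a visit missed. The reference in 9.3 to sessions as the protocol describes them might be read as admitting footnote c, but the same phrase requires all three explicitly. At best it is ambiguous, and two analysts could build different sets.

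**Conclusion.** The point holds as an inconsistency with limited reach. Footnote c and the three-session requirements in 6.1.2.1, 9.1.1, 9.2.1, 9.3 and 9.4.4.1 cannot all apply to a patient who is never discharged before PORT. Section 9 counts that patient as a non-completer and leaves the patient out of the per-protocol set.

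The size depends on a frequency that the documents do not give. For assumed rates of 1% to 10%, with 90% completing applicable sessions, the chance of passing the completion rule falls from 82% to between 78% and 44%. Excluding one to six patients lowers an NDURE per-protocol delay rate of 25% to between 24.0% and 18.5% if all are delayed, and to between 24.7% and 22.8% if half are.

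The RCT primary modified intention-to-treat analysis, its 83% power and the feasibility study's primary endpoint of accrual are untouched. What is affected is a secondary feasibility criterion and the secondary per-protocol analyses.

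**What to change.** Reconcile Table 1 footnote c with 6.1.2.1, 6.4, 8.4.1, 9.1.1, 9.2.1, 9.3 and 9.4.4.1. No position is taken here on which schedule is right.

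If footnote c stands:

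- define completion, and per-protocol membership in the NDURE arm, as attending every session that Table 1 schedules for that patient;
- state how usual-care patients enter the per-protocol set;
- report, by arm, the number of patients whose Visit 4 was omitted under footnote c.

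The cost is small wording changes in both the protocol and the analysis sections. Discharge status before PORT must also be captured for every patient, because discharge date is not among the clinical items listed in 8.2.2 and 8.3. Session attendance is already logged (6.2.1, 6.4). The new definition changes what the 13-of-15 rule counts, so the probabilities in 9.2.1 should be restated as referring to completion of scheduled sessions.
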